14.3. Analysis Populations

Safety Population:

All subjects who were administered any test article excluding subjects who drop out prior to administering any test article. At least one observation should be recorded.

Per-Protocol Population:

All subjects who have successfully completed all visits and did not substantially deviate from the protocol as determined by the trial cohort review committee prior to database hard lock (Per-Protocol Population). Justification of excluding subjects with protocol deviations in the Per-Protocol Population set will be documented in a memo to file.

Intent-to-Treat (ITT) Population:

All randomized subjects regardless of actual treatment and subsequent withdrawal from study or deviation from protocol. At least one observation should be recorded.

14.4. Level of Statistical Significance

All planned primary analyses for this study will be conducted with a 2-sided type I family wise error rate of 5%. The Bonferroni¹² method will be used to adjust for the number of primary hypotheses tested. Secondary hypotheses will be tested separately with a 2-sided type I error rate of 5% individually.

14.5. Primary Analysis

CLUE Vision Scores

Vision scores after approximately 2-weeks in the optimized lenses will be analyzed using a linear mixed model. Baseline vision scores, event (visit 1: baseline, visit 2: 1-wk non-optimized, visit 3: 1-wk optimized and visit 4: 2-wk optimized), strata (hyperope and myope) and the interaction between event and strata will be included in the model as fixed effects. Other covariates such as age, gender and add power may be included when appropriate. Site will be included as a random effect (G-side). Residual errors between measurements within the same subject across event will be model using one of the following:

- Unstructured (UN)
- Compound Symmetric (CS)

• Heterogenous Compound Symmetric (CSH)

The structure that returns the lowest corrected Akaike's Information Criterion (Keselman et al. 1998)¹³ will be selected as the structure that best fits the data. The Kenward and Roger method will be used for the calculation of the denominator of degrees of freedom.¹⁴

Primary hypothesis 1:

The null and alternative hypothesis for CLUE vision to test for superiority of the Test lens relative to the pre-defined threshold of 40 for myopes is as follows:

$$H_o$$
: $\mu_{Test} \le 40$
 H_A : $\mu_{Test} > 40$

Superiority will be declared if the lower limit of the 95% confidence interval of the adjusted mean for the Test lens is greater than 40. i.e. $P(\mu_{Test} > 40) \ge 0.975$.

Primary hypothesis 2:

The null and alternative hypothesis for CLUE vision to test for superiority of the Test lens relative to the pre-defined threshold of 32 hyperopes is as follows:

$$H_o$$
: $\mu_{Test} \le 32$
 H_A : $\mu_{Test} > 32$

Superiority will be declared if the lower limit of the 95% confidence interval of the adjusted mean for the Test lens is greater than 32. i.e. $P(\mu_{Test} > 32) \ge 0.975$.

LogMAR Visual Acuity

Binocular, high luminance, high contrast visual acuity on logMAR scale after approximately 2-weeks in the optimized lenses will be analyzed using a linear mixed model. Position(distance/intermediate/near) will be included as the only fixed effect. Site will be included as random effect (G-side). Other baseline characteristics known of importance such as age, gender and add power may be included as covariates when appropriate. The covariance between residual errors from the same subject across different positions will be selected based on the finite-sample corrected Akaike's Information Criterion (Keselman et al. 1998). Covariance structures considered may include: Homogenous compound symmetry (CS) and Unstructured covariance structure (UN). The structure that returns the lowest Akaike Information Criteria Corrected (AICC) will be selected as the structure that best fit the data. The Kenward and Roger method will be used for the calculation of the denominator of degrees of freedom. Acres of the calculation of the denominator of degrees of freedom.

Primary hypothesis 3:

The null and alternative hypothesis for binocular distance HLHC visual performance to test for superiority of the Test lens relative to the pre-defined threshold of 0 logMAR is as follows:

$$H_o$$
: $\mu_{Test} \ge 0 \log MAR$
 H_A : $\mu_{Test} < 0 \log MAR$

Superiority will be declared if the upper limit of the 95% confidence interval of the adjusted mean for the Test lens is below 0 logMAR. i.e. $P(\mu_{Test} < 0) \ge 0.975$.

Primary hypothesis 4:

The null and alternative hypothesis for binocular near HLHC visual performance to test for superiority of the Test lens relative to the pre-defined threshold of 0.17 logMAR is as follows:

$$H_o$$
: $\mu_{Test} \ge 0.17 \log MAR$
 H_A : $\mu_{Test} < 0.17 \log MAR$

Superiority will be declared if the upper limit of the 95% confidence interval of the adjusted mean for the Test lens is below 0.17 logMAR. i.e. $P(\mu_{Test} < 0.17) \ge 0.975$.

Primary hypothesis 5:

The null and alternative hypothesis for binocular distance HLHC visual performance to test for superiority of the Test lens relative to the pre-defined threshold of 0.17 logMAR is as follows:

$$H_o$$
: $\mu_{Test} \ge 0.17 \log MAR$
 H_A : $\mu_{Test} < 0.17 \log MAR$

Superiority will be declared if the upper limit of the 95% confidence interval of the adjusted mean for the Test lens is below 0.17 logMAR. i.e. $P(\mu_{Test} < 0.17) \ge 0.975$.

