2.3. Hypotheses

All primary hypotheses must be met in order to satisfy the study objective.

Primary Hypotheses

- 1. After approximately 2 weeks of wear in the optimized lenses, the mean overall quality of vision score with the Test lens will be statistically better than 40 points on CLUE scale for myopic subjects.
- 2. After approximately 2 weeks of wear in the optimized lenses, the mean overall quality of vision score with the Test lens will be statistically better than 32 points on CLUE scale for hyperopic subjects.

- 3. After approximately 2 weeks of wear in the optimized lenses, the binocular, high-luminance, high-contrast distance (4 M) logMAR visual acuity of the test lens will be statistically better than 0.00 logMAR. This will be determined using ETDRS LogMAR acuity testing charts.
- 4. After approximately 2 weeks of wear in the optimized lenses, the binocular, high-luminance, high-contrast intermediate (64 cm) logMAR visual acuity of the test lens will be statistically better than +0.17 logMAR. This will be determined using Guillon/Poling LogMAR acuity testing charts.
- 5. After approximately 2 weeks of wear in the optimized lenses, the binocular, high-luminance, high-contrast near (40 cm) logMAR visual acuity of the test lens will be statistically better than +0.17 logMAR. This will be determined using Guillon/Poling LogMAR acuity testing charts.

Secondary Hypotheses

Secondary hypotheses will be tested for the hyperopes and the myopes separately.

- 1. After approximately 2 weeks of wear in the optimized lenses, the mean overall quality of vision CLUE score for Test lens will be non-inferior to the baseline score measured for habitual correction. A non-inferiority margin of -5 will be used.
- 2. After approximately 2 weeks of wear in the optimized lenses, the mean comfort CLUE score with the Test lens will be non-inferior to the baseline score measured for habitual correction. A non-inferiority margin of -5 will be used.
- 3. After approximately 2 weeks of wear in the optimized lenses, the mean lens handling CLUE score with the Test lens will be non-inferior to the baseline score measured for habitual correction. A non-inferiority margin of -5 will be used.

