14.6. Secondary Analysis

CLUE Vision, Comfort and Handling Scores

Vision, Comfort and Handling scores after approximately 2-weeks in the optimized lenses will be analyzed separately using a linear mixed model. event (visit 1: baseline, visit 2: 1-wk non-optimized, visit 3: 1-wk optimized and visit 4: 2-wk optimized), strata (hyperope and myope) and the interaction between event and strata will be included in the model as fixed effects. Other covariates such as age, gender and add power may be included when appropriate. Site will be included as a random effect (G-side). Residual errors between measurements within the same subject across event will be model using one of the following:

- Unstructured (UN)
- Compound Symmetric (CS)
- Heterogenous Compound Symmetric (CSH)
- Spatial Power (SP(POW))

The structure that returns the lowest corrected Akaike's Information Criterion (Keselman et al. 1998)¹³ will be selected as the structure that best fits the data. The Kenward and Roger method will be used for the calculation of the denominator of degrees of freedom.¹⁴

Hypothesis Testing

The null and alternative hypotheses for non-inferiority are as follows and will be conducted separately for each strata (hyperopes and myopes) and CLUE vision, comfort and handling:

$$H_0$$
: $\Delta \le -5$
 H_0 : $\Delta > -5$

Where Δ is the change from baseline to 2-week follow-up (2-week follow up minus baseline). Non-inferiority of the 2-week follow-up CLUE score relative to the baseline CLUE scores of subjects' habitual lens was concluded if the lower limit of the 95% CI was above -5 (Pr: 2 – wk minus baseline > -5,) > 0.975.

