14.10. Procedure for Reporting Deviations from Statistical Plan

The analysis will be conducted according to that specified in above sections. There are no known reasons for which it is planned to deviate from these analysis methods. If for any reason a change is made, the change will be documented in the study report along with a justification for the change.

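### The primary CLUE vision model uses the baseline score both as covariate and as visit-1 response, so two of its three covariance structures cannot be fitted and the third understates the standard error

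*Combined protocol and SAP*

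**What the plan says.** Section 14.5 fits a linear mixed model to the CLUE vision scores. Its fixed effects are "Baseline vision scores, event (visit 1: baseline, visit 2: 1-wk non-optimized, visit 3: 1-wk optimized and visit 4: 2-wk optimized", then strata and the event-by-strata interaction. Residuals within a subject across event may be UN, CS or CSH. "The structure that returns the lowest corrected Akaike's Information Criterion" is selected. "Site will be included as a random effect (G-side"), and Kenward-Roger degrees of freedom are used. The myope hypothesis is met if "the lower limit of the 95% confidence interval of the adjusted mean for the Test lens is greater than 40"; the hyperope rule is the same with 32.

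Baseline CLUE is collected at Visit 1 on habitual lenses (section 7.2), so the covariate and the visit-1 response are the same number.

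Section 14.6 models vision, comfort and handling with the same event levels but no baseline covariate: these scores "will be analyzed separately using a linear mixed model. event (visit 1: baseline, visit 2: 1-wk non-optimized", and so on.

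Neither section says what to do if a structure does not converge. For any departure from the plan, section 14.10 says: "If for any reason a change is made, the change will be documented in the study report along with a justification for the change".

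**The concern.** A variable cannot be a predictor and, unchanged, one of the responses it predicts. At visit 1 a slope of 1 explains the response perfectly.

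- **UN and CSH** give visit 1 its own variance. The fit can shrink that variance towards zero and raise the likelihood without limit.
- **CS** has one common variance, so the fit stays finite. The artificially small visit-1 residuals are averaged into it, and the standard error of the visit-4 mean comes out too small.

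The primary CLUE result would then rest on a choice made after fits have failed. Section 14.8 has hyperope results summarised once all hyperopes have completed, possibly before myopes are enrolled, so that choice could also follow a look at half of the data.

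**Working it through.** **Inputs.** Table 7 CLUE vision SDs, baseline and 2-week: hyperopes 14.71 and 18.65, myopes 15.43 and 20.73. Target completers: 35 and 45 (section 14.2). Baseline to follow-up correlation r: 0.3 and 0.5, the Table 9 scenarios. Assumed, because the documents do not say: visits 2 and 3 have the visit-4 SD, correlations between follow-up visits are 0.5 to 0.8, data are complete, stratum baselines are equal, and adjusted means are taken at the overall baseline mean.

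**The plan's own figures.** The plan states no standard error for the mixed model. The CLUE rows of Table 8 (80.1% at n = 18, 80.9% at n = 22) are closely reproduced from Table 7 as 80.8% and 80.7% with one-sided alpha 0.01, which supports the inputs. At the stated two-sided 0.01 the power is 71.3% and 71.5%; that is a separate matter.

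**1. UN and CSH.** At slope 1, all 80 visit-1 residuals are zero. Cutting the visit-1 residual SD tenfold lowers REML -2logL by (80 - 3) x ln 100 = 77 x 4.605 = 354.6; the 3 are two visit-1 stratum means and the slope. One simulated dataset shows it:

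| Visit-1 residual SD | 10 | 1 | 0.1 | 0.01 | 0.001 |
|---|---|---|---|---|---|
| CSH, REML -2logL | 2454 | 2100 | 1745 | 1390 | 1036 |

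CS on the same data gives 2574. UN contains CSH and falls by the same amount per step. Maximum likelihood behaves likewise, as does a model with site variance of 25.

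The AICC penalty cannot stop this. With n* = 320 - 9 = 311 and d covariance parameters including site, 2d x n*/(n* - d - 1) is 22.9 for UN (d = 11), 12.3 for CSH (d = 6) and 6.1 for CS (d = 3). UN costs 16.8 points more than CS and CSH 6.2 more, against a gain of 355 per step. AICC has no minimum.

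**2. CS, no site variance.** Pooled over strata:

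- Follow-up variance: (35 x 18.65² + 45 x 20.73²)/80 = 393.9
- Baseline variance: (35 x 14.71² + 45 x 15.43²)/80 = 228.6
- Covariance: r x (35 x 14.71 x 18.65 + 45 x 15.43 x 20.73)/80 = 299.9r

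Without visit-1 rows the slope is b = 299.9r/228.6. With them, the four-visit subject mean is 0.25 x baseline + 0.75 x follow-up mean, so the slope becomes b* = 0.25 + 0.75b. The pooled variance is the average of three follow-up visits and visit 1, and SE = sqrt(variance/45), ignoring a small slope term.

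| | r = 0.3 | r = 0.5 |
|---|---|---|
| b, then b* | 0.394, 0.545 | 0.656, 0.742 |
| Variance without visit 1: 393.9 - 228.6b² | 358.5 | 295.5 |
| Follow-up residual variance at b*: above + 228.6(b* - b)² | 363.7 | 297.2 |
| Visit-1 residual variance: 228.6(1 - b*)² | 47.3 | 15.2 |
| Pooled with visit 1: (3 x follow-up + visit 1)/4 | 284.6 | 226.7 |
| Myope SE with / without visit 1 | 2.51 / 2.82 | 2.24 / 2.56 |
| Reduction | 10.9% | 12.4% |

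REML simulation gives the same SEs and reductions of 10.9 to 12.5%. The follow-up correlation hardly matters.

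**3. Is the smaller SE real?** No. In 40,000 simulated trials per setting (follow-up correlation 0.7), the empirical SD of the myope estimate was 3.03 with or without visit-1 rows at r = 0.3, and 2.90 either way at r = 0.5. One-sided error with the true mean at the threshold, over all settings:

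| | Double use | Without visit-1 rows | Nominal |
|---|---|---|---|
| Myopes, 95% interval | 5.2-6.4% | 3.3-4.2% | 2.5% |
| Myopes, 99% interval | 1.6-2.4% | 0.8-1.1% | 0.5% |
| Hyperopes, 95% interval | 3.5-4.5% | 2.0-2.7% | 2.5% |

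The 99% row is there because section 14.4 says Bonferroni "will be used to adjust for the number of primary hypotheses tested" while section 14.5 uses 95% intervals. Varying the visit 2-3 SDs by 20% either way gives SE reductions of 9.6 to 13.0%.

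**4. Site.** Under CS with visit-1 rows, the estimated between-subject residual and site variances are 0.75² = 9/16 of those without. In one dataset site variance was 22.86 against 40.64 (ratio 0.5625), and the SE 2.53 against 3.10. With 6 to 12 assumed sites and 5 to 10% of variance between sites, the reduction was 12 to 18%. Holding site variance equal in both fits cut it to 5% in one dataset (2.94 against 3.10), but section 14.5 estimates site variance within the model.

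**5. Decisions.** Myopes pass under double use if the observed mean exceeds 44.4-45.0 (95%) or 45.8-46.5 (99%). With the covariate only, the limits are 45.1-45.6 and 46.7-47.4; with the section 14.6 mean model, 45.8-45.9 and 47.7-47.8. With true mean 55.1 and SE 20.73/sqrt(45) = 3.09, the chance of an observed mean between 44.4 and 45.9 is 0.12%, and between 45.8 and 47.8 it is 0.78%.

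**The case against.** The best defence is that section 14.5 opens by referring to scores after about two weeks, so the event list may be carried over from section 14.6 and the response meant to be follow-up visits only. But section 14.6 opens with the same phrase for a model that must contain visit 1 to estimate change from baseline. The phrase removes nothing, and no other text does.

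A second defence is that a structure that fails to fit returns no AICC, so CS is chosen without any change to the plan. That is possible; how software reacts is outside the documents. It leads straight to the understated SE. If the degenerate fit were accepted instead, myope error would be 2.4 to 3.7%, near nominal, but the slope would be forced to 1 with no valid maximum. The two consequences are alternatives and should not be added together.

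Three points stand:

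- The practical effect is small. Double use alone, against the covariate-only model, moves the myope pass line by about 0.6 to 0.7 points at 95%. At a mean of 55.1 that changes the result with probability 0.03 to 0.05% (95% interval) or 0.20 to 0.37% (99%).
- Not all excess error comes from double use. Covariate-only CS already exceeds 2.5% for myopes.
- The error rates assume equal stratum baselines. With Table 7's 42.9 and 45.5, and means taken at the overall baseline, myope error is 7.2 to 10.6% with double use against 4.4 to 7.2% without. The unstated baseline reference value is a separate contributor.

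**Conclusion.** The concern holds and should be fixed. That UN and CSH have no likelihood maximum is algebra and needs no planning assumption: two of the three prespecified structures for a primary endpoint cannot be fitted as written.

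The 11 to 12% SE reduction is conditional on CS being used, the Table 7 SDs, correlations of 0.3 to 0.5 and no site variance. The move to CS is an inference, because the plan states no fallback.

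A wrong conclusion is unlikely at the planning values: 15.1 points above the myope threshold is 5.3 SEs (15.1/2.82) to 6.7 SEs (15.1/2.24). Section 2.3 also says "All primary hypotheses must be met in order to satisfy the study objective", so these single-endpoint errors are not the study's false-success rate.

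**What to change.** Give baseline one role, and settle it before any hyperope results are read.

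- **Option A (preferred).** Drop the baseline covariate from section 14.5 and use the section 14.6 mean model: visits 1 to 4 as response; event, strata and their interaction; visit-4 mean per stratum. AICC selection among UN, CS and CSH can stay. In simulation without site variance, myope error was 3.0 to 3.5% (95% interval) and hyperope error 1.7 to 2.4%.
- **Option B.** Keep the covariate, limit the response to visits 2 to 4, and state that each stratum's adjusted mean is taken at its own baseline mean. Under CS this gives myope error of 3.7 to 5.2%, because the SE treats the baseline mean as known, so it removes less of the excess.

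The cost is one sentence in section 14.5 and a somewhat wider, more accurate interval for myopes. Data collection, sample size and the covariance selection rule do not change.

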14.2. Sample Size Justification

This study was designed and powered to demonstrate that the binocular high luminance high contrast, visual performance (logMAR) of the Test lens at distance (4 meters), intermediate (64 cm) and near (40 cm) after 2-week of lens wear in the optimized lenses is superior to 0.00, +0.17 and +0.17 logMAR, respectively. Additionally, this study was also powered to show that CLUE vision scores for the Test lens for the hyperopic population is greater than 32 points and greater than 40 points for the myopic population. The sample size calculation included

two historical studies, and Previous hyperopic data was not available for the Test lens, therefore, data from was used because it evaluated lenses with a similar lens design on a hyperopic population. Data from was used for the myopic population since this study evaluated lenses with the same lens design and similar material as the current Test lens on a population of myopic subjects.

Table 6: Historical Binocular High Luminance High Contrast Visual Performance – 2-Week Follow-up

Chart Position	Mean	SD*	Minimum	Maximum
Distance (4 M)	-0.048	0.0943	-0.220	0.280
Intermediate (64 cm)	-0.015	0.1183	-0.240	0.320
Near (40 cm)	0.097	0.1318	-0.200	0.500

^{*}SD: Standard Deviation

Table 7: Historical CLUE Scores – 2-Week Follow-up

CLUE Domain	Strata	Baseline	2-Week Follow-up
		Mean (SD*)	Mean (SD*)
Vision	Hyperope	45.5(14.71)	47.3(18.65)
	Myope	42.9(15.43)	55.1(20.73)
Comfort	Hyperope	50.7(19.70)	60.9(22.38)
	Myope	54.5(20.39)	62.7(21.95)
Handling	Hyperope	50.9(17.26)	56.6(21.12)
	Myope	56.9(16.49)	70.6(18.02)

^{*}SD: Standard Deviation

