Sample size calculations for each primary endpoint were carried out using a 2-sided one sample mean t-test, with a family wise error rate of 5%. The calculation was performed using the POWER¹¹ procedure in SAS Version 9.4⁸. The Bonferroni¹² method was used to adjust the type I error for multiple primary hypotheses $\alpha = \frac{0.05}{5} = 0.01$. A power analysis was also performed for each secondary hypothesis to test for non-inferiority of the 2-week follow-up relative to the baseline assessment with respect to CLUE vision, comfort and handling scores. The power analysis was performed for each secondary hypothesis separately using the POWER procedure and 2-sided t-test for paired means with alpha=0.05. The power Analysis was performed for different scenarios of intraclass correlation and effect sizes. The sample size required for all primary endpoints is displayed in Table 8, while the power analysis for the secondary endpoints is located in Table 9.

^{**}This summary included data from both

Table 8: Sample Size Estimates for Primary Endpoints

Endpoint	Power	Sample Size
Visual Acuity - Distance (4 M)	80.6%	42
Visual Acuity - Intermediate (64 cm)	80.1%	7
Visual Acuity - Near (40 cm)	80.7%	36
CLUE Vision Scores – Hyperopes	80.1%	18
CLUE Vision Scores – Myopes	80.9%	22

Table 9: Power Analysis for Secondary Endpoints

Endpoint	Strata	correlation	Effect size	Power
Vision – CFB*	Hyperope N=35	0.3	1	42.3%
			3	75.0%
		0.5	1	65.5%
			3	86.0%
	Myope N=45	0.3	3	78.1%
			5	91.7%
		0.5	3	88.2%
			5	97.1%
Comfort – CFB*	Hyperope N=35	0.3	3	58.4%
			5	75.0%
		0.5	3	70.8%
			5	86.3%
	Myope N=45	0.3	3	67.8%
			5	83.9%
		0.5	3	80.1%
			5	92.9%
Handling – CFB*	Hyperope N=35	0.3	3	64.8%
			5	81.2%
		0.5	3	76.9%
			5	90.8%
	Myope N=45	0.3	3	82.6%
			5	94.3%
		0.5	3	92.0%
			5	98.5%

^{*}CFB = Change from baseline (calculated as 2-week follow-up minus baseline)

Represents conservative power estimate based on the most conservative effect size and intraclass correlation.

While only 42 subjects are required to complete the study based on the sample size calculation, the plan is to compare the data from this study to another study which is similar in design and sample size and is assessing a marketed multifocal toric lens. Therefore, the sample size was increased in order to perform a meta-analysis at a later date. Moreover, as shown in Table 9, a

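### The primary success rule is not uniquely defined: 14.2 and 14.4 apply Bonferroni (two-sided 0.01), while all five rules in 14.5 use unadjusted 95% intervals; Table 8 and the H4/H5 labels also need correcting

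*Combined protocol and SAP*

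**What the plan says.** - **Success rule (2.3):** "All primary hypotheses must be met in order to satisfy the study objective". There are five: CLUE vision above 40 in myopes (H1) and above 32 in hyperopes (H2), and binocular acuity at distance (H3), intermediate (H4) and near (H5).
- **Level, analysis (14.4):** a two-sided family-wise rate of 5%, and the Bonferroni "method will be used to adjust for the number of primary hypotheses tested".
- **Level, sample size (14.2):** calculations "were carried out using a 2-sided one sample mean t-test, with a family wise error rate of 5"%. The Bonferroni "method was used to adjust the type I error for multiple primary hypotheses", giving 0.05/5 = 0.01.
- **Decision rules (14.5):** for the CLUE scores, "Superiority will be declared if the lower limit of the 95% confidence interval of the adjusted mean for the Test lens" exceeds 40 or 32. The acuity rules mirror this with the upper 95% limit. Each of the five is restated as a probability of at least 0.975.
- **Table 8:** 42, 7, 36, 18 and 22 subjects for about 80% power each, followed by "While only 42 subjects are required to complete the study based on the sample size calculation".
- **H4 and H5:** section 2.3 has "binocular, high-luminance, high-contrast intermediate (64 cm) logMAR visual acuity of the test lens will be statistically better than +0.17 logMAR" as H4, and near at +0.17 as H5. Section 14.5 writes H4 as near and H5 as distance, both at 0.17.

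**The concern.** Two-sided 0.01 corresponds to a 99% interval (one-sided 0.005). The plan does not print that figure, but it follows directly from 0.05/5. The 0.975 repeated in 14.5 shows that the 95% there is not shorthand for an adjusted interval. Two analysts following the same plan could therefore reach opposite verdicts. Since all five hypotheses must be met, a single endpoint whose limit clears its threshold at 95% but not at 99% decides the study.

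Two further faults sit in the same text. Table 8 may not follow from the level stated for it, and 42 is the size for one endpoint although success needs all five. Read literally, 14.5 also contains no rule for intermediate acuity, and its H5 (distance below 0.17) is implied by H3 (distance below 0).

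Timing adds some weight. The hyperope read in 14.8 is descriptive, but it will show the complete H2 data. A level chosen after it would be open to challenge.

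**Working it through.** **Inputs.** Means and SDs are from Tables 6 and 7, thresholds from 2.3, and planned completers from 14.2. The method is the one-sample t-test: power = P(T > t crit), where T is noncentral t with n − 1 df and noncentrality (difference/SD) × √n.

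| Endpoint | Difference from threshold | SD | Table 8 n | Planned n |
|---|---|---|---|---|
| Distance | 0 − (−0.048) = 0.048 | 0.0943 | 42 | 80 |
| Intermediate | 0.17 − (−0.015) = 0.185 | 0.1183 | 7 | 80 |
| Near | 0.17 − 0.097 = 0.073 | 0.1318 | 36 | 80 |
| CLUE, hyperopes | 47.3 − 32 = 15.3 | 18.65 | 18 | 35 |
| CLUE, myopes | 55.1 − 40 = 15.1 | 20.73 | 22 | 45 |

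**Step 1: reproduce Table 8.** For distance, noncentrality is 0.048/0.0943 × √42 = 3.30. The critical value is 2.42 at one-sided 0.01 (power 80.6%) and 2.70 at two-sided 0.01 (power 72.2%).

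| Endpoint | Printed n (power) | Power, one-sided 0.01 | Power, two-sided 0.01 | n for 80%, two-sided 0.05 | n for 80%, two-sided 0.01 |
|---|---|---|---|---|---|
| Distance | 42 (80.6%) | 80.6% | 72.2% | 33 | 49 |
| Intermediate | 7 (80.1%) | 80.1% | 66.2% | 6 | 9 |
| Near | 36 (80.7%) | 80.7% | 72.2% | 28 | 42 |
| Hyperopes | 18 (80.1%) | 80.8% | 71.3% | 14 | 21 |
| Myopes | 22 (80.9%) | 80.7% | 71.5% | 17 | 26 |

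Of one-sided 0.05, 0.025, 0.01 and 0.005, only 0.01 returns all five printed sizes. The printed hyperope power is not matched exactly: rounding of the inputs allows 80.5 to 81.1%. Three levels are therefore in play: 95% intervals in the rules, 99% in the text and 98% behind the table.

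**Step 2: the zone where the sections disagree.** Margin beyond the threshold = t × SD/√n at planned n. For distance this is 1.990 × 0.0943/√80 = 0.0210 at 95%, and 2.640 × 0.0943/√80 = 0.0278 at 99%.

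| Endpoint | Margin 95% / 99% | Observed means that pass at 95% and fail at 99% |
|---|---|---|
| Distance | 0.0210 / 0.0278 | −0.028 to −0.021 logMAR |
| Intermediate | 0.0263 / 0.0349 | 0.135 to 0.144 logMAR |
| Near | 0.0293 / 0.0389 | 0.131 to 0.141 logMAR |
| Hyperopes | 6.41 / 8.60 | 38.4 to 40.6 points |
| Myopes | 6.23 / 8.32 | 46.2 to 48.3 points |

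**Step 3: power for all five at planned n** (distance, intermediate, near, hyperopes, myopes).
- 95% intervals: 99.4, 100, 99.8, 99.7, 99.8%; product 98.7%.
- 99% intervals: 97.0, 100, 98.9, 97.9, 98.3%; product 92.3%.
- The 98% level behind Table 8 would give 96.1%.

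The products assume independence. Simulations with assumed correlations of 0 to 0.8 between acuity positions and CLUE within subject give about 99% and about 92.5 to 94%. Passing at 99% implies passing at 95%, so the verdicts differ in about 5 to 6% of trials.

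**Step 4: the 42.** With 42 subjects, split 18/24 by assumption, joint power is 70.7% (95%) or 31.9% (99%) under independence, and about 72 to 79% or 37 to 48% at correlations of 0.3 to 0.8.

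**Step 5: error control.** When all five must pass, false study success cannot exceed the level of the one test whose null is true: 2.5% one-sided with 95% intervals, 0.5% with 99%. Only if endpoints were claimed singly could 95% intervals give up to 5 × 0.025 = 12.5%.

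**The case against.** The strongest reply is that nothing is lost either way. Error is controlled under both readings, planned enrolment is ample for both, and the verdicts differ in only about one trial in twenty if the historical means hold. This is correct, and it rules out any claim of inflated error. It does not supply the missing rule, and a study the synopsis calls confirmatory needs one success criterion fixed in advance. Section 14.10 provides only for documenting changes, so it cannot settle which rule was planned.

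Some narrower points have force:
- The hypotheses in 14.5 are directional, so in 14.2 the slip may be the word two-sided rather than the table. However, 14.4 also says two-sided, and one-sided 0.01 matches neither 14.4 nor 14.5. Either the wording or the table must change.
- Table 8 is already listed by endpoint, and the study does not run at 42. The joint power at 42 describes a trial nobody plans and rests on an assumed split. What remains is that the sentence about 42 is misleading under the all-five rule.
- The H4/H5 error is a copying slip. Section 2.3, Table 8 and the 14.2 statement that acuity "is superior to 0.00, +0.17 and +0.17 logMAR, respectively" all recover the intended thresholds.
- Removing Bonferroni relaxes a stated standard. Both repairs are coherent, and the choice belongs to the sponsor.

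**Conclusion.** The concern holds. The plan gives two incompatible levels for the same five decisions and does not say which governs. This must be settled; the Table 8 and labelling faults are smaller corrections to the same text.

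At planned size the choice moves the required margin by about 2 CLUE points (8.60 − 6.41 = 2.19 in hyperopes, 8.32 − 6.23 = 2.09 in myopes) and by 0.007 to 0.010 logMAR. It moves joint power from 98.7% to 92.3% under independence. At the stated two-sided 0.01, Table 8's sizes give 66 to 72% power, not 80 to 81%.

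These figures rest on the historical means and SDs and on simple t intervals. The planned mixed models, with site effects and Kenward-Roger degrees of freedom, would shift them somewhat. The conflict between the sections does not depend on any of them.

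**What to change.** 1. **Choose one level and state it everywhere.** Given 2.3, the simpler course is to say in 14.4 that success requires all five primary hypotheses, each tested with a two-sided 95% interval (one-sided 0.025) without multiplicity adjustment. Then delete Bonferroni from 14.2 and 14.4 and leave the levels in 14.5 unchanged. If endpoints will be claimed singly, keep Bonferroni and change all five rules in 14.5 to 99% intervals and 0.995.
2. **Relabel in 14.5:** H4 as intermediate (64 cm) below +0.17 and H5 as near (40 cm) below +0.17, as in 2.3.
3. **Restate Table 8 at the chosen level** as per-endpoint sizes for 80% power (distance, intermediate, near, hyperopes, myopes): 33, 6, 28, 14, 17 at two-sided 0.05, or 49, 9, 42, 21, 26 at two-sided 0.01. Do not present the largest as the number the study needs. Joint power there is only about 49% under independence with assumed hyperope/myope splits of 14/19 or 21/28.
4. **Replace the sentence about 42** with joint power at the planned 80/35/45: about 98.7% (95% intervals) or 92.3% (99% intervals), stating the independence assumption.

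These changes are best made before the hyperope read in 14.8. The cost is wording in 14.2, 14.4 and 14.5 and a recalculated table; enrolment, visits and data collection are unaffected.
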